5.3 Other Outcomes of Interest

- Changes in the ordinal WHO scale from baseline over 14 days
- Length of hospital stay until day 28 in survivors.
- Proportion of participants progressing to mechanical ventilation on day 7 and day 14
- Proportion of participants requiring ICU treatment on day 7 and 14
- Length of ICU stay until day 28
- Ventilator-free days until day 28
- All-cause mortality (time from randomisation to death within four weeks)
- Changes in biomarker levels until day 14: CRP, LDH, D-dimer, ferritin, IL-6, lymphocyte count
- Time to virological clearance of SARS-CoV-2 by PCR from upper or lower respiratory tract samples (time from enrolment to first of 2 negative assays at least 12 hours apart)
- Proportion of patients receiving additional anti-inflammatory treatment such as tocilizumab or immunoglobulins within 14 days
- Time to defervescence (temperature <38.0°C sustained for at least 48 hours)
- Time to clinical improvement (defervescence, normalization of oxygen saturation (>93%) and respiratory rate) until day 28
- Duration of supplemental oxygen until day 28
- Incidence of acute kidney injury classified on the basis of the worst serum creatinine according to the KDIGO classification, and changes of serum creatinine and estimated glomerular filtration rate (eGFR, estimated with the CKD-EPI equation) from baseline
- In a subgroup of patients (in Basel and optional in other centers) the pharmacokinetics and pharmacodynamics of conestat alfa in COVID-19 patients will be characterized by measuring the concentration of conestat alfa and the activity of C1INH, inflammatory cytokines and proteins (such as C4d, C5a, sC5-b9, IL-10) and parameters of the contact activation and coagulation cascade (such as factor XII and pre-kallikrein). In addition, changes of urinary markers of renal injury (such as NGAL, KIM-1, osteopontin and clusterin) from baseline will be analysed.

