6.2.2 Blinding procedures

Participants, treating physicians, nurses, investigators and DSMB members will not be blinded.

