9.2.3 Assessment of other outcomes of interest

- The following assessments will be performed during the study: changes in WHO ordinal scale, ICU admission/discharge date, mechanical ventilation start/end date, admission/discharge date, all-cause mortality at 4 weeks
- The receipt of additional anti-inflammatory treatments such as tocilizumab will be recorded within 14 days
- Vital signs will be recorded during 14 days until discharge to determine the time to defervescence and clinical improvement
- For the analysis of virological clearance of SARS-CoV-2, samples from the upper or lower respiratory tract will be collected at baseline (if not already performed on admission) to confirm SARS-CoV-2 infection and again on day 4-7 and day 14/discharge (only when discharged on day 10-13). Subsequently, samples will be analysed at the central laboratory of the study site using a quantitative assay according to validated standard in-house procedures. A negative result will be confirmed by a second test at least 12 hours apart.
- For the analysis in changes of biomarker levels CRP- LDH, D-dimer, IL-6 and lymphocytes will be measured in blood samples collected on day 0, 1-3 and every second day afterwards until day 14 or discharge. Blood samples will be sent to and analysed by validated methods in the central laboratory of respective study sites according to standard in-house procedures
- The incidence of acute kidney injury will be evaluated according to the KDIGO classification. Baseline creatinine will be defined as a concentration obtained within a 12-month period before admission and considered to be representative of the baseline kidney function according to the judgment of the treating physician. If this reference value is not available, the minimum of either serum creatinine at the time of admission or study inclusion, or in patients without chronic kidney disease, a calculated serum creatinine concentration using the MDRD equation will be used.

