9.3 Procedures at each visit

9.3.1 Split into subtitles by type of visit

Visit 1, Screening (Day -1 or day 0):

Informed consent will be obtained before any study-specific tests or evaluations will be performed.

- Patients who are admitted to the medical ward with confirmed or suspected SARS-CoV-2 infection will be screened within 72 hours after admission on the ward. Screening will be based on routinely available data and laboratory tests with only the pregnancy test as study-specific intervention/test if necessary before screening of the patients. Results from prior tests that will be used for screening potentially eligible subjects will be recorded in the eCRF.
- Selection of potential participants according to inclusion and exclusion criteria.
- Explanation of patient information including study purpose and signature of informed consent form.
- Study enrolment
- Assignment of the trial subject identification number
- Pregnancy test if applicable.
- Eligibility check (in- and exclusion criteria)
- Randomisation, which can either occur on the same day of hospital admission or within 72 hours after hospital admission.

Visit 2, Intervention period (Day 0)

- Assessment of demographics, medical history and concomitant medication
- Assessment of vital signs including respiratory rate.
- Assessment of WHO ordinal scale and need for oxygen supplementation
- Collection of blood (12ml) for analysis of ferritin, IL-6, D-Dimer, C1INH concentration, and in Basel (optional for other centers): collection of blood (5ml) and urine (5ml) for the analysis of complement proteins, parameters of the contact activation and coagulation system, renal injury markers, and inflammatory cytokines. Routine full blood count, coagulation and biochemistry studies will only be performed if results from prior tests on the same day are not available.
- Assessment of reference serum creatinine
- Virology testing (quantitative SARS-CoV-2 PCR) on a nasopharyngeal sample if not already performed before inclusion into the study. This is optional for other centers except Basel.
- Following randomisation, participants in the active treatment group will receive 8400 U of conestat alfa as slow intravenous injection. The time of dosing and the dose will be recorded. Subsequently, 4200 U will be administered every 8 hours in the active trial group.
- AEs occurring after the administration will be recorded.

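### The KDIGO reference creatinine is left to the judgment of an unblinded physician and scheduled after randomisation, so the exploratory AKI incidence is open to arm-dependent choice of its denominator

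*Protocol*

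**What the plan says.** Protocol section 5.3 lists among the other outcomes of interest: "Incidence of acute kidney injury classified on the basis of the worst serum creatinine according to the KDIGO classification". Section 9.2.3 defines the reference: "Baseline creatinine will be defined as a concentration obtained within a 12-month period before admission", with the condition that it is "considered to be representative of the baseline kidney function according to the judgment of the treating physician". It gives no rule for a patient with several eligible values and no criterion for representativeness.

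The fallback begins: "If this reference value is not available, the minimum of either serum creatinine at the time of admission or study inclusion". It then adds, with a further 'or', an MDRD-calculated value for patients without chronic kidney disease.

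On blinding, section 6.2.2 states: "Participants, treating physicians, nurses, investigators and DSMB members will not be blinded". On timing, section 9.3.1 lists under Visit 1: "Randomisation, which can either occur on the same day of hospital admission or within 72 hours after hospital admission". The item "Assessment of reference serum creatinine" appears under Visit 2 (day 0). Section 11.4.3 says that other outcomes of interest are analysed descriptively and exploratorily.

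**The concern.** KDIGO grading on creatinine compares the worst value with a reference. The worst value is a laboratory result. Here the reference is a selection, made by someone who may know the allocation. If higher prior values tend to be judged representative in one arm, fewer patients in that arm cross the threshold, with the same kidney function.

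Section 6.2 relies on randomisation and objective endpoints to limit bias in this open-label trial, and section 6.2.3 names no other measure. A discretionary denominator weakens that protection for AKI. Protection from renal damage is also part of the rationale in section 3.1, so a reader of the results may give AKI incidence some weight, and a pilot's exploratory findings may inform later studies (section 3.7).

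**Working it through.** **1. Who chooses, and with what knowledge.**
- Choice: treating physician, by judgment (9.2.3).
- Blinding: treating physicians are not blinded (6.2.2).
- Timing: randomisation is in Visit 1, which is also the screening column of the schedule in 9.1; the reference creatinine is in Visit 2 (9.3.1).
- Safeguard: nothing requires the value to be fixed before allocation or by a person unaware of the arm.

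The post-randomisation timing follows from the visit order, not from a sentence that says so. Both visits may fall on day 0, and the item is listed before the first dose. The arm is known from allocation, however, not from the first dose.

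**2. The fallback.** The phrase "the minimum of either serum creatinine at the time of admission or study inclusion, or in patients without chronic kidney disease" followed by the MDRD value can be read in at least three ways:
- one minimum over all listed values;
- the measured minimum in patients with chronic kidney disease and MDRD in those without;
- a free choice between the two in those without.

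The first two are deterministic and the third is not. The text does not settle which applies.

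**3. Can the mechanism move incidence?** The plan states no AKI rate, so there is no figure to reproduce. The following is an illustration on assumed inputs, none from the documents. Let worst/reference creatinine be lognormal with median 1.15 and log-SD 0.30, and use only the 1.5-fold criterion. If the chosen reference is k times higher,

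P(AKI) = 1 − Φ[(ln(1.5k) − ln 1.15) / 0.30].

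| k | z | AKI |
|---|---|---|
| 1.00 | 0.886 | 18.8% |
| 1.10 | 1.203 | 11.4% |
| 1.15 | 1.352 | 8.8% |
| 1.20 | 1.493 | 6.8% |

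If only part of one arm is affected, at k = 1.20:
- a quarter of the arm: 0.75 × 18.8 + 0.25 × 6.8 = 15.8%, a gap of 3.0 points;
- half of the arm: 0.50 × 18.8 + 0.50 × 6.8 = 12.8%, a gap of 6.0 points.

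For scale, with 80 and 40 patients and a common rate of 18.8%, the standard error of the difference is √[0.188 × 0.812 × (1/80 + 1/40)] = 7.6 points. The quarter-arm gap is 3.0/7.6 = 0.4 standard errors.

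**4. A second illustration.** This is a simulation with identical kidney function in both arms. It assumes two eligible prior values per patient with log-SD 0.05 to 0.20 around the true baseline, and a worst value with median 1.15 times baseline and log-SD 0.25. In a share of patients the higher prior value is taken in the conestat alfa arm and the lower one in the control arm.
- Share 25%: artefactual gap 1.3 to 5.1 points.
- Share 50%: 2.6 to 10.1 points.
- Reference fixed without regard to arm: expected gap zero.

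Both exercises show only that the mechanism can produce a difference. They do not estimate one for this trial.

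**The case against.** The strongest reply has five parts.

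*The physician cannot aim at an outcome.* When the reference is assessed on day 0, the worst later creatinine is unknown. This stands as a limit: nobody can see which choice creates or removes an AKI event. A general leaning towards higher or lower references by arm would still be possible.

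*The values themselves are fixed.* Candidate references predate admission, so treatment cannot change them. A reader might infer that any bias would be undetectable. The documents do not support that: laboratory reports are source data (12.1.2), monitors have access to them (12.3), and eCRF entries carry an audit trail (12.2). Prior values could be re-abstracted and AKI recomputed under a fixed rule. The check would be partial, because section 9.2.3 does not require all eligible values to be captured.

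*The fallback may be deterministic.* A reader might infer a second free choice through MDRD. That holds on only one of the possible readings, so what remains is an ambiguity to remove.

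*Some renal history is already reviewed before allocation.* Prior results used for screening are entered in the eCRF at Visit 1, and chronic renal disease is one of the eligibility risk factors (7.1). This is fair, but nothing makes those entries the AKI reference.

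*AKI carries little inferential weight.* It is one of many exploratory outcomes, alongside changes in creatinine and eGFR and urinary injury markers (5.3). Section 11.4.1 calculates changes from baseline from Visit 2, day 0. This stands and limits the importance of the point.

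**Conclusion.** The point holds in a limited form. Sections 9.2.3, 6.2.2 and 9.3.1 together allow the AKI reference to be chosen by judgment with the arm known. Incidence can therefore differ between arms for a reason unrelated to kidney function; the documents do not show that it will.

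The size cannot be derived from the plan. A reader might take from the illustration that AKI incidence would be roughly halved, since k = 1.15 gives 8.8% against 18.8%, a relative fall of 53%. That would need a reference 15% higher in every patient of one arm, on assumed distributions. Patients with one or no prior value leave little room for choice, although judging a lone value unrepresentative would arguably bring the fallback into play.

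The primary endpoint, the secondary endpoints and the interim decisions do not use this value. It is a minor design weakness, worth correcting because the correction is nearly free.

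**What to change.** 1. In section 9.3.1, move the assessment of reference creatinine from Visit 2 to Visit 1, ahead of randomisation. Require the value, or the entry that none is available, to be recorded in the eCRF before allocation. This step alone removes the dependence on arm.
2. Preferably, replace the judgment in section 9.2.3 by a fixed selection rule, for example the most recent eligible pre-admission value.
3. Reword the fallback so that the measured minimum and the MDRD value are applied in one stated way to all patients. MDRD need not be dropped: relying only on the lower of the admission and inclusion values could hide AKI already present on entry.

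Cost: a few words in two sections and one eCRF field moved, with no new sample or visit. Where no measured pre-admission value exists, the Visit 1 entry need only say so. The small downside is that a fixed rule will occasionally use an unrepresentative historical value, equally in both arms.

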9.2.4 Assessment of safety outcomes

9.2.4.1 Adverse events

Participants will be followed for adverse events during 4 weeks after enrolment. After the end of clinical follow-up there is no requirement to actively collect AEs including death.

Adverse events and clinical course including death within 4 weeks will be assessed by a structured telephone interview after 4 weeks. If necessary, medical charts will be reviewed, discharge summaries will be or the patients' general practitioner will be contacted regarding specific follow-up information. Every effort will be made to contact the trial subject and obtain complete data for follow-up. Conditions that started before signing informed consent will be recorded as medical history. Conditions that started or deteriorated after signing informed consent will be documented as AE. Definition of AE and SAE will be found in Section 10.

All AEs will be assessed and documented by the investigators according to seriousness, intensity, causal relationship with study treatment, action taken with study treatment (e.g. withdrawal), specific treatment for AE and outcome. In addition, time of onset and AE duration will be recorded. Procedures are defined in Section 10. AEs will be recorded on the respective eCRF pages.

Participants will be asked about any new events/complaints during the admission and at 4 weeks.

In addition, participants are asked to report any new events including hospital admission to the study team.

9.2.4.2 Laboratory parameters

Previous studies of conestat alfa have not shown any influence of conestat alfa on laboratory parameters. Hence, we will not perform additional laboratory monitoring exceeding routine laboratory controls planned by the treating team. If laboratory findings reveal abnormal values, they will be documented and reported as an AE if deemed clinical significant by the treating team or the investigators.

9.2.4.3 Vital signs

No study specific vital signs will be assessed. All patients will be monitored regarding blood pressure, heart rate, respiratory rate and oxygen saturation as per standard operating procedures for the treatment of COVID-19 patients.

9.2.5 Assessments in participants who prematurely stop the study

Patients who are withdrawn from the study will remain in the trial for the purpose of follow-up and data analysis and will be followed as planned with the following exceptions.

- Patients, who withdraw consent for all study measures, will be asked to have assessments performed as appropriate for the final 4 week study visit (i.e. a structured telephone interview). The same approach applies for all active study participants if the trial is stopped early. Patients who withdraw consent are at liberty to refuse any or all individual components of the final assessment.
- Patients who are withdrawn because they have not received any study medication will not be followed up and will not receive a final study assessment.

Patients who discontinue the study because of safety concerns will be followed as planned. Patient with a type I allergic reaction will be referred to our Allergy department for further work-up.

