9.2 Assessments of outcomes

9.2.1 Assessment of primary outcome

For the analysis of the primary endpoint, illness severity will be assessed on each day after enrolment (worst status) with the use of the WHO Ordinal Scale for Clinical Improvement (score 0 will be omitted and score 6 and 7 will be combined) and the score on day 7 will be analysed stratified by its baseline value.

Patient State	Descriptor	Score
Uninfected	No clinical or virological evidence of infection	0
Ambulatory	No limitation of activities	1
	Limitation of activities	2
Hospitalized Mild disease	Hospitalized, no oxygen therapy	3
	Oxygen by mask or nasal prongs	4
Hospitalized Severe Disease	Non-invasive ventilation or high-flow oxygen	5
	Intubation and mechanical ventilation	6
	Ventilation + additional organ support – pressors, RRT, ECMO	7
Dead	Death	8

Figure 4: WHO ordinal scale for clinical improvement. For the current study, score 0 will be omitted, and score 6 and 7 will be combined.

The worst score on a given day (between 0:00 and 24:00 hours) will be used for the categorization

Patient State	Description	Score
---------------	-------------	-------

Outpatient	No limitation in activities	1
	Limitation in activities	2
Hospitalized Mild disease	No oxygen therapy	3
	Oxygen by mask or nasal prongs	4
Hospitalized Severe disease	Non-invasive ventilation or high-flow oxygen	5
	Intubation, mechanical ventilation +/- additional organ support	6
Death	Death	7

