9.2.2 Assessment of secondary outcomes

- For the analysis of time to clinical improvement of at least 2 points in the WHO Ordinal Scale for Clinical Improvement, clinical severity will be assessed every day until day 14 according to the Scale with the worst status for that day recorded
- For the analysis of the proportion of patients alive and not having required invasive or non-invasive ventilation at 14 days after enrolment, admission to ICU with invasive or non-invasive ventilation or death will be assessed every day until day 14.
- For the analysis of the proportion of patients with ALI within 14 days after enrolment, PaO₂/FiO₂ will be determined daily until day 14. This is only relevant for patients with arterial blood gas sampling performed in the ICU or rarely on the ward.

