11.4 Planned Analyses

11.4.1 Datasets to be analysed, analysis populations

A review of the database will be conducted in a blinded manner shortly before the database will be locked, and any decisions made at that meeting (blinded Data Review Meeting) concerning the statistical analysis, e.g., additional outcomes and populations, pooling of sites for efficacy analysis, will be documented in the Statistical Analysis Plan (SAP).

Missing data for the primary endpoint will be imputed by means of the Last-observation-carried-forward (LOCF) method.

Safety Population: The Safety Population is defined as all patients who received at least one dose of conestat alfa. Statistical analyses will be based on the actual treatment the patient received.

Full Analysis Set/Intent-to-Treat Population: The FAS/ITT Population is defined as all patients who are randomly allocated to a study arm. Statistical analyses will be based on the treatment arm to which the patient was allocated.

For quantitative data, the number of patients with non-missing information, means, medians, standard

deviations and extremes will be determined. For qualitative data, absolute and relative frequencies will be calculated. Moreover, changes from baseline (V2, d0) will be calculated.

Per Protocol Population: The PP Population is defined as all patients in the FAS/ITT Population who complete the study and who do not have any major protocol violations, including the following:

- Patients who had major inclusion/exclusion criteria violations.

Sufficient compliance is expected because of IV administration of the IMP.

The PP Population will be determined by a blinded review in the Data Review Meeting (DRM) of the data prior to database lock.

The primary efficacy analysis will be based on the FAS/ITT Population in this superiority trial; an additional efficacy analysis will be performed on the PP Population. The Safety Population will be used for all safety analyses.

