11.4.4 Interim analyses

Two interim analyses after 40 and 80 patients are planned according to the Pocock adjusted levels $\alpha_p = 0.0221$. Based on the results of an interim analysis the sample size can be adjusted (Lehmacher, Wassmer, 1999). There are no prespecified futility margins, but the DSMB can recommend stopping the study in the case of insufficient interim results.

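### Section 9.2.5 replaces planned follow-up by the week-4 interview for active participants at an early trial stop, so day-7 and day-14 outcomes of consenting patients are not secured

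*Protocol*

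**What the plan says.** Protocol section 9.2.5 starts from the principle that withdrawn patients "will be followed as planned with the following exceptions". The first exception concerns patients who withdraw consent for all study measures: they "will be asked to have assessments performed as appropriate for the final 4 week study visit (i.e. a structured telephone interview"). The next sentence, inside the same exception, reads "The same approach applies for all active study participants if the trial is stopped early".

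The endpoints need earlier data.

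- **Primary outcome (9.2.1):** the WHO scale is recorded daily as the worst status, and "the score on day 7 will be analysed stratified by its baseline value". Section 9.3 (visit 5) adds a short telephone call to score patients discharged before day 7 as 1 or 2.
- **Time to improvement (9.2.2):** "clinical severity will be assessed every day until day 14 according to the Scale with the worst status for that day recorded".
- **Alive without ventilation (9.2.2):** "admission to ICU with invasive or non-invasive ventilation or death will be assessed every day until day 14".
- **Acute lung injury (ALI, 9.2.2):** the PaO2/FiO2 ratio is also followed daily to day 14.

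On the analysis side, section 11.4.1 states "The FAS/ITT Population is defined as all patients who are randomly allocated to a study arm", and sections 11.4.1 and 11.5 impute a missing primary value by LOCF. Early stopping is foreseen: "Two interim analyses after 40 and 80 patients are planned according to the Pocock adjusted levels" (11.4.4). Section 11.3 lets the DSMB recommend a stop for insufficient interim results, and section 2.9 lists further reasons.

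**The concern.** Two different situations receive one rule. A patient who withdraws consent limits what may be collected. A participant who is active when the trial stops has set no such limit, yet planned follow-up is replaced in the same way. The result is odd within 9.2.5 itself, because patients who discontinue over safety concerns are followed as planned and so receive more follow-up than active participants at an early stop.

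At stake is the primary endpoint of the last patients enrolled. They remain in the FAS/ITT set, so a day-7 score that could have been observed becomes an LOCF value. Entry requires an expected inpatient stay over the next three calendar days (7.1). A score carried from days 0 to 2 will therefore normally be an inpatient score of 3 or higher, whereas the day-7 score could be 1 or 2.

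**Working it through.** **1. Reading the rule.** The sentence on early stop sits inside an exception to planned follow-up, so it substitutes for that follow-up rather than adding a call. No other section keeps day-7 scoring or daily recording to day 14 going after a stop.

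**2. What the week-4 contact can recover.** Visit 7 (9.3) covers adverse events, the WHO scale, ICU admission and ventilation, with review of charts and discharge summaries where necessary.

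| Item | After an early stop under 9.2.5 |
|---|---|
| Day-7 score 3 to 7 | In charts; retrievable but not required |
| Day-7 score 1 versus 2 after discharge | Needs the separate call near day 7; not secured |
| Daily scale to day 14 | Partly retrievable |
| Ventilation, ICU status, blood gases | Largely in charts; retrieval not guaranteed |
| Serious adverse events | Still followed to resolution or stabilisation (10.1.1, 10.1.3) |

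**3. Number of patients affected.** The accrual rate is not stated. Assumption: 120 patients evenly over 10 to 11 months, from the planned dates in the synopsis (first participant in 7/2020, last out 6/2021).

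- Rate: 120 / (11 × 30.4) = 0.36 per day; 120 / (10 × 30.4) = 0.39 per day.
- Not yet at day 7: rate × 7 = 2.5 to 2.8.
- Not yet at day 14: rate × 14 = 5.0 to 5.5.
- At twice the rate: 5.0 to 5.5 and 10.0 to 11.1.
- At three times the rate: 7.5 to 8.3 and 15.1 to 16.6.

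Set against the 40 patients of the first look, the group before day 7 equals 2.5/40 = 6% at even accrual over 11 months and 7.5/40 = 19% at three times that rate. Against the 80 patients of the second look, the figures are 3% and 9%.

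**4. The plan's own design figures.** For a 1-point effect, SD 1.5, two-sided 0.05 and 80% power, the t-test needs 36.3 per arm. Dividing by the Wilcoxon efficiency 3/π = 0.955 gives 38.0, which matches the stated 2 × 38. The level 0.0221 at three equally spaced looks gives an overall two-sided error of 0.0501, so 0.05 is reproduced. Neither figure is disputed.

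**5. Chance that an efficacy stop occurs.** The inputs are those of section 11.2, treated as a difference in means, with three equal stages of 40 patients split 2:1 (26.67 and 13.33) and combined by the inverse-normal method.

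- Drift per stage: (1/1.5) × √(26.67 × 13.33 / 40) = 0.667 × 2.981 = 1.99.
- Critical value for 0.0221 two-sided: 2.289.
- First look: 1 − Φ(2.289 − 1.99) = 0.38.
- By the second look: the combined statistic has mean 1.99 × √2 = 2.81 and correlation 0.71 with the first. The chance of crossing at either look is 0.72.
- With no effect, the chance at the first look is 0.0221, about 2%.

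**The case against.** The strongest reply is that little is truly lost. Section 9.2.5 does not forbid earlier outcome recording. Most of those affected are inpatients whose oxygen and ventilation status is charted, visit 7 permits chart review, and section 9.2.4.1 asks for every effort to complete follow-up data. This stands in part: retrieval is possible but conditional, nothing requires it for day 7 or day 14, and scores 1 and 2 after discharge are the least recoverable.

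Four stronger readings are tempting, and the documents do not support them.

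- **The primary and secondary endpoints are lost outright.** They are not secured, which is weaker. Events before the stop are already recorded, and live discharge, ventilation and blood gases can be read from records.
- **Safety follow-up shrinks to one call.** Serious adverse events are followed to resolution or stabilisation, including those ongoing at study termination. After discharge, the week-4 interview was already the main planned safety contact.
- **All carried-forward scores precede any treatment effect.** The last dose is scheduled 64 hours after the first (8.2.1), so patients stopped on days 3 to 6 have largely finished dosing.
- **The interim decision itself is damaged.** A look after 40 or 80 patients presumably uses patients with an available endpoint. Those affected are then mainly enrolled around the stop and are not behind the boundary crossing.

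It is also fair that the 38% and 72% hold only if the 1-point effect is true, and section 11.2 says that reliable information on the clinical course is lacking.

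**Conclusion.** The point holds as a defect in the wording of 9.2.5. A stated rule would replace observable primary outcomes by LOCF values, and leave day-14 outcomes to discretionary retrieval, for patients who have not withdrawn consent and who remain in the FAS/ITT set.

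The size is modest: about 2.5 to 3 patients before day 7 and about 5 before day 14 at assumed even accrual, rising to about 5 to 8 and 10 to 17 at two to three times that rate. The effect is on the completeness of the final data after a stop. The situation is not remote under the design assumptions, but how probable it is depends on the true effect. The change is worth making because the loss is avoidable and the remedy is cheap.

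**What to change.** In section 9.2.5, separate early trial stop from withdrawal of consent and delete the sentence that equates them. State instead that, after an early stop, every randomised participant who has not withdrawn consent keeps the planned outcome recording:

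- the daily WHO score, with ventilation and ICU status;
- the day-7 score, including the telephone call if discharged;
- day-14 status;
- the week-4 contact.

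Add that these observed data enter the final analysis. Study-specific blood and urine sampling need not continue.

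The cost is a short text change and up to four more weeks of already planned outcome recording for a few patients.
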